**Organ Class and Preferred Term**

- All/Treatment-Emergent Adverse Events Leading to Study Drug Dose Reduction by System Organ Class and Preferred Term
- All/Treatment-Emergent Adverse Events Leading to Study Drug Interruption by System Organ Class and Preferred Term
- All/Treatment-Emergent Adverse Events by System Organ Class, Preferred Term and Cycle
- All/Treatment-Emergent Adverse Events with Grade 3 or Higher by System Organ Class, Preferred Term and Cycle

Also, the number and percentage of subjects with TEAEs that emerged during time from the study drug approval date to switching to commercial tazemostat will be calculated by System Organ Class and Preferred Term for FL Cohort Subjects who Continued Study after Study Drug Approval Date.

In counting numbers of subjects by causal relationship or severity, each subject will be counted only once for that categories. If a subject experienced relevant TEAEs more than once, the subject will be categorized according to the prioritizations of (“related” > “not related”]) for the causal relationship and (“Grade 5” > “Grade 4” > “Grade 3” > “Grade 2” > “Grade 1”) for the severity.

### 5.6.3 Laboratory Values

Laboratory results will be summarized using Système International (SI) units, as appropriate.

For all quantitative parameters listed in [protocol Section 9.5.1.5.4](#) Safety Assessments (Laboratory Measurements), the actual value and the change from baseline to each post baseline visit and to the end of treatment will be summarized by visit using descriptive statistics. Qualitative parameters listed in [protocol Section 9.5.1.5](#) will be summarized using frequencies (number and percentage of subjects), and changes from baseline to each post baseline visit and to end of treatment will be reported using shift tables. Percentages will be based on the number of subjects with both non-missing baseline and relevant post baseline results.

CTCAE ver.4.03 will be used to identify subjects with treatment-emergent markedly abnormal laboratory values (TEMAVs). Except for phosphate, a TEMA V is defined as a post baseline value with an increase from baseline to a grade of 2 or higher. For phosphate, a TEMA V is defined as a postbaseline value with an increase from baseline to a grade of 3 or higher. When displaying the incidence of TEMA Vs, each subject will be counted once in the laboratory parameter high and in the laboratory parameter low categories, as applicable. TEMA Vs will be summarized for study overall.

The measured values for quantitative data will be displayed over time using Box plot.

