7.4.2.2 Summary of Safety in Clinical Study Conducted in Japan

As of 31 July 2017, tazemetostat 800 mg has been administered orally by single dose in Cycle 0 Day 1 and then continuous BID to 7 subjects enrolled in the Japanese Phase 1 study. The most frequently reported treatment-related TEAEs were thrombocytopenia (3 subjects; 43%), anemia, dry skin, rash, and dysgeusia (2 subjects each; 29%), constipation, fatigue, gastritis, hypoalbuminemia, insomnia, leukopenia, muscle spasms, nausea, neutropenia, and stomatitis (1 subject each; 14%). The treatment-related TEAEs of Grade 3 or higher were thrombocytopenia (2 subjects; 29%) and anemia (1 subject; 14%). There were no SAEs related to study drug.

Eisai Confidential Page 28 of 71 FINAL: 29 Jan 2021

Eisai Confidential Page 29 of 167

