9.4.2.2 Comparator Drug

Not applicable.

Eisai Confidential Page 37 of 71

a: Tolerability of Grade 2 toxicities will be judged by the investigator or subinvestigator.

b: Dose interruption and reduction are not necessary for Grade 3 thrombocytopenia, anemia and Grade 3 or 4 leukopenia, lymphopenia and laboratory abnormalities that are not clinically relevant. Initiate optimal medical management for nausea, vomiting, and/or diarrhea prior to any study treatment interruption or dose reduction and follow the dose reduction and interruption instructions when it cannot be controlled.

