9.5.1.5.1 ADVERSE EVENTS

An AE is any untoward medical occurrence in a patient. An AE does not necessarily have a causal relationship with the medicinal product. For this study, the study drug is tazemetostat.

The criteria for identifying AEs in this study are:

- Any unfavorable and unintended sign (including an abnormal laboratory finding), symptom, or disease found after the time of informed consent, whether or not considered related to the investigational product (Note: Every sign or symptom should not be listed as a separate AE if the applicable disease [diagnosis] is being reported as an AE)
- Any new disease or exacerbation of an existing disease. However, worsening of the primary disease should be captured under efficacy assessments as disease progression rather than as an AE.
- Any deterioration in protocol-required and nonprotocol-required measurements of a laboratory value or other clinical test (eg, ECG or x-ray) that results in symptoms, a change in treatment, or discontinuation of study drug
- Recurrence of an intermittent medical condition (eg, headache) not present pretreatment (Baseline)
- An abnormal laboratory test result should be considered an AE if the identified laboratory abnormality leads to any type of intervention, withdrawal of study drug, or withholding of study drug, whether prescribed in the protocol or not

All AEs, regardless of relationship to study drug or procedure, should be recorded beginning from the time the subject signs the study ICF through the final observation visit. When subject needs to receive other anti-tumor therapy within 30 days after the final study drug administration, final observation must be conducted before initiation of other anti-tumor therapy. SAEs will be collected until the final observation visit.

Any laboratory abnormality considered to constitute an AE should be reported on the CRF. Abnormal laboratory values should not be listed as separate AEs if they are considered to be part of the clinical syndrome that is being reported as an AE. It is the responsibility of the investigator or subinvestigator to review all laboratory findings in all subjects and determine if they constitute an AE. Medical and scientific judgment should be exercised in deciding whether an isolated laboratory abnormality should be classified as an AE.

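### SAP 5.6.3 gives no subject counts by CTCAE grade for laboratory values, so the number of subjects with Grade 3-4 laboratory cytopenia cannot be read from the planned tables and may be understated

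*SAP*

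**What the plan says.** **Laboratory tables.** SAP 5.6.3 applies CTCAE v4.03 to laboratory data for one purpose, to identify TEMAVs. For all parameters but one, "a TEMA V is defined as a post baseline value with an increase from baseline to a grade of 2 or higher". Phosphate is the exception, with a threshold one grade further up (Grade 3). In the incidence table, "each subject will be counted once in the laboratory parameter high and in the laboratory parameter low categories", and no breakdown by grade is mentioned.

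Quantitative parameters otherwise get values and changes from baseline summarised by visit (SAP 5 includes the minimum and maximum). In addition, "The measured values for quantitative data will be displayed over time using Box plot". The statement that "changes from baseline to each post baseline visit and to end of treatment will be reported using shift tables" belongs to the sentence on qualitative parameters. Protocol 9.7.1.8.3 draws the same line and leaves the details of the TEMAV definition to the SAP.

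**Adverse event tables.** SAP 5.6.2 tabulates treatment-emergent events by system organ class, preferred term and CTCAE grade, and Grade 3 or higher events by cycle. Each subject is counted at the worst grade.

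**What becomes an adverse event.** Protocol 9.5.1.5.1 includes abnormal laboratory findings in its general AE criterion. It adds: "An abnormal laboratory test result should be considered an AE if the identified laboratory abnormality leads to any type of intervention", or to withdrawal or withholding of study drug. An isolated laboratory abnormality is otherwise left to medical judgement. No grade makes recording compulsory.

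**Dose rules.** Protocol Table 2, footnote b: "Dose interruption and reduction are not necessary for Grade 3 thrombocytopenia, anemia and Grade 3 or 4 leukopenia, lymphopenia and laboratory abnormalities". The footnote then adds a qualifier about lack of clinical relevance. The neutropenia row keeps the dose unchanged when ANC is at or above 0.75×10⁹/L.

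**The concern.** The laboratory data are the objective record of cytopenia, but the plan never turns them into a count of subjects at Grade 3 or Grade 4. That count can come only from the AE tables, which hold only what the investigator chose or was obliged to record.

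Table 2 bears on this because withholding drug is one of the triggers for AE recording. Where Table 2 does not call for withholding, that trigger need not be met. A Grade 3 platelet fall with no other intervention can then be absent from every graded AE table and indistinguishable from Grade 2 in the TEMAV table.

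Safety is a secondary objective, and the earlier studies point to cytopenia as the main source of severe events. A severe-event count that depends on site recording practice is a weak basis for describing it. The SAP is finer elsewhere: SAP 5.6.5 reports QTcF prolongation at three separate thresholds.

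**Working it through.** The plan states no figure for this point, so there is none to reproduce. The check traces a case through the planned tables and then illustrates the loss of information.

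**1. Trace one case.** Suppose a subject's platelets fall to Grade 3 from a lower baseline grade, with no transfusion, no withholding and no symptoms.

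| Planned output | What it shows |
|---|---|
| TEMAV table (SAP 5.6.3) | One count under platelets low, the same as for a Grade 2 fall |
| By-visit summaries and box plots (SAP 5, 5.6.3) | The low value may be the visit minimum; no count of subjects by grade |
| Shift tables (SAP 5.6.3) | Stated for qualitative parameters only |
| TEAE tables by grade (SAP 5.6.2) | Shown as Grade 3 if recorded as an AE, otherwise absent |

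**2. Ambiguity of the TEMAV count.** Assume 6 of 21 subjects have a low-platelet TEMAV: 6/21 = 28.6%. The number at Grade 3-4 can then be any integer from 0 to 6, that is 0% to 28.6%. The figure 21 is the planned number of efficacy-evaluable subjects (8 + 13); the number treated could be larger.

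**3. Is cytopenia the relevant toxicity?** From Protocol 7.4:
- Japanese Phase 1: the related Grade 3 or higher events were thrombocytopenia, 2/7 = 28.6% (exact 95% CI 3.7% to 71.0%), and anemia, 1/7 = 14.3%.
- Overseas Phase 2: anemia, 17/266 = 6.4%, was the only Grade 3 or higher event of any causality in at least 5% of subjects.
- Overseas Phase 1: the single dose-limiting toxicity was Grade 4 thrombocytopenia.
- Any-grade related events, overseas Phase 2: nausea 38/266 = 14.3%, fatigue 35/266 = 13.2%, thrombocytopenia 19/266 = 7.1%.

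Cytopenia is therefore the main severe toxicity, but not the most frequent toxicity overall.

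**4. Illustration of possible understatement.** Expected Grade 3 or higher cases appearing in the AE tables = 21 × p × (1 − u). Here p is the true rate and u the share not recorded as AEs. Both are assumptions.

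| p | Expected cases, 21p | u = 0 | u = 25% | u = 50% | u = 100% |
|---|---|---|---|---|---|
| 5% | 1.05 | 1.05 | 0.8 | 0.5 | 0 |
| 10% | 2.1 | 2.1 | 1.6 | 1.05 | 0 |
| 2/7 | 6.0 | 6.0 | 4.5 | 3.0 | 0 |

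Nothing in the documents fixes u. A worst-grade laboratory table would show every case in which the low count was measured, whatever the value of u.

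**The case against.** The strongest reply is that the graded AE tables already do this job. That is partly right, and it rules out several stronger readings.

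- A reader might infer that severe cytopenias are tabulated by grade nowhere. That is true of laboratory values only; cytopenias recorded as AEs appear by grade in the SAP 5.6.2 tables.
- A reader might infer that the AE rules exempt Grade 3 platelet falls. They do not. An abnormal laboratory finding is itself within the AE criteria, the investigator must review all laboratory results, and intervention of any type is a broad trigger. Footnote b governs dosing, not AE recording, and how far its clinical-relevance qualifier reaches is unclear. Non-recording is permitted by discretion, not directed. ANC below 0.75×10⁹/L calls for interruption and so meets the AE rule.
- A reader might take 2/7 × 21 = 6 as missed cases. But 2/7 is a rate of events that were recorded as AEs, so it measures no under-recording.
- A reader might use the overseas result, in which every Grade 3 or higher event except anemia was below 5%, as a ceiling here. That figure pools 115 solid-tumour subjects. Below 5% of 266 allows up to 13 subjects; if all had lymphoma, the rate would be 13/151 = 8.6%.
- A reader might infer that results would not be comparable with earlier studies. Those results are reported as TEAEs and SAEs, so the planned AE tables are the like-for-like comparison.

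Two further points have some force. With cohorts of about 8 and 13, visit minima would reveal deep falls. The separate table shells (SAP 11) might also split TEMAVs by grade. But minima do not count subjects, and nothing in the SAP text requires the split.

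**Conclusion.** The point holds as a gap in reporting. As written, SAP 5.6.3 yields one TEMAV category and no worst-grade or grade-shift table for blood counts. The graded AE tables fill the gap only as far as isolated abnormalities are recorded at the investigator's discretion. The number of subjects with Grade 3-4 laboratory cytopenia therefore cannot be read from the planned tables.

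The direction of any error is towards understatement. Its size is unknown: it could be nil, or it could cover every case that needed no intervention. No planned estimate is shown to be wrong, and the efficacy analysis is unaffected. This is a worthwhile, low-cost improvement to a descriptive safety analysis. The conclusion assumes that the unseen table shells follow the SAP text. It takes the Table 2 dose rules as given and offers no view on them.

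**What to change.** In SAP 5.6.3:

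1. Split the TEMAV incidence table into Grade 2, Grade 3 and Grade 4, with each subject at the worst grade per parameter and direction (Grades 3 and 4 for phosphate, whose threshold is already Grade 3).
2. Add a shift table from baseline CTCAE grade to worst post-baseline grade for at least platelets, hemoglobin, neutrophils, lymphocytes and leukocytes, by cohort and overall.
3. State that scheduled and unscheduled values from first dose to final observation are used. The SAP is silent on this, and Table 2 footnote e recommends checks at least every 7 days during interruptions, which by-visit summaries need not capture.

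The cost is SAP wording and a few extra tables. Scheduled values are already collected and must already be graded to identify TEMAVs; whether unscheduled results are in the database should be confirmed. The downside for the sponsor is that laboratory-based Grade 3-4 rates may look less favourable than the AE-based rates. No clinical rule changes.

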#### 5.6.4 Vital Signs

Descriptive statistics for vital signs parameters (diastolic and systolic blood pressure, pulse rate, body temperature), and weight and changes from baseline will be presented by visit, End of Treatment and Final Observation.

The measured values will be displayed over time using Box plot.

#### 5.6.5 12-lead ECGs

ECG assessments were performed at each visit. Descriptive statistics for ECG parameters and changes from baseline will be presented by visit, End of Treatment and Final Observation. Shift tables will present changes from baseline in ECG interpretation (categorized as normal; abnormal, not clinically significant; and abnormal, clinically significant) to end of treatment by visit. In addition, the number (percentage) of subjects with at least 1 post baseline abnormal ECG result QTc Fridericia during the treatment period will be summarized. Clinically abnormal ECG results in QTc Fridericia will be categorized as follows:

Absolute QTc interval prolongation:

- QTc interval >450 ms
- QTc interval >480 ms
- QTc interval >500 ms

Change from baseline in QTc interval:

- QTc interval increases from baseline >30 ms
- QTc interval increases from baseline >60 ms

#### 5.6.6 Other Safety Analyses

##### **ECOG PS :**

ECOG-PS will be summarized by scale at each visit and by highest postbaseline scale.

## 5.7 Exploratory Analyses

Exploratory analyses may be conducted as appropriate. Any exploratory analyses that are performed will be appropriately titled and labeled as exploratory and will be clearly distinguished from planned analyses when results are reported in the Clinical Study Report.

## 6 INTERIM ANALYSES

No interim analyses are planned for this study.

## 7 CHANGES IN THE PLANNED ANALYSES

Changes in the planned analyses for protocol are as follows:

- Calculation of 95% CIs for ORR have been added ([section 5.4.1](#)).
- Subgroup analyses have been added. Both 90% CIs and 95% CIs for ORR(independent reviewer assessment) will be calculated for all and each subgroup ([section 5.3.4](#)).

## 8 DEFINITIONS AND CONVENTIONS FOR DATA HANDLING

The data will be handled as follows. The sponsor will determine how to handle all data prior to data base lock.

### 8.1 PHARMACOKINETIC DATA HANDLING

#### 8.1.1 Lower Limit of Quantification of Tazemetostat Plasma Concentration

The LLOQ of tazemetostat plasma concentrations is 1.00 ng/mL.

#### 8.1.2 BLQ Handling for Calculation of PK Parameters

Not applicable

#### 8.1.3 BLQ Handling for Developing Concentration-Time Profiles

Not applicable

### 8.1.4 Handling of Anomalous Concentration Values

The handling of anomalous concentration values will follow the guidance in the Eisai manual 302-104.01-MNL for non compartmental PK analysis (Version Date: 28 Jun 2018).

### 8.1.5 General Rules for Presentation of Drug Concentrations and PK Parameters

When presenting individual/raw (raw, hereafter) values and summary statistics, the following rule will be applied: for drug concentrations, all summary statistics (mean, median, and standard deviation [SD]) will have 3 significant digits.

Variable	Unit	N	Digit rule	Raw/ Minimum/ Maximum	Mean Median	SD	Geometri c Mean	CV (%)
Tazemetostat concentration	ng/mL	X	Significant digits	3	3	3	-	-

## 8.2 OTHER DATA HANDLING

### Baseline

Baseline is defined as the last non-missing value observed prior to the first dose of study drug for a given parameter. For any Baseline value of 0, the subject's corresponding Percent Change from Baseline will not be included in the summary statistics tables.

### Handling of Missing data

No imputation will be performed for missing data.

## 9 PROGRAMMING SPECIFICATIONS

The rules for programing derivations and dataset specification are provided as separate documents.

## 10 STATISTICAL SOFTWARE

PK Analysis will be performed using SAS for Windows (ver.9.2 or later), WinNonlin (Professional version 6.2.1 or later), Pharsight Knowledgebase Server (version 3.0 or later), Microsoft Excel (97 or later) and S-PLUS (6.1J or later for Windows).

Statistical analyses and summaries will be performed by Takumi Information Technology using SAS for Windows (ver.9.2 or later), and Microsoft Excel (2003 or later). Analyses will be conducted by using validated standard programs or double programming. For analyses needed in data review, single programming will be used.

## **11 MOCK TABLES, LISTINGS, AND GRAPHS**

The study table, listing and graph (TLG) shells will be provided in a separate document, which will show the content and format of all tables, listings, and graphs in detail.

## **12 REFERENCES**

There is no reference.

## 13 APPENDICES

### 13.1 National Institute for Health: Common Terminology Criteria for Adverse Events (CTCAE) Version 4.03

National Cancer Institute (NCI) Cancer therapy evaluation program Common Terminology Criteria for Adverse Events (CTCAE) version 4.0 May 2009 (v4.03 June 2010) is available online at:

[https://evs.nci.nih.gov/ftp1/CTCAE/CTCAE\\_4.03/CTCAE\\_4.03\\_2010-06-14\\_QuickReference\\_5x7.pdf](https://evs.nci.nih.gov/ftp1/CTCAE/CTCAE_4.03/CTCAE_4.03_2010-06-14_QuickReference_5x7.pdf)
